PAD attenuates both life expectancy and the quality of life as it increases the risk of cardiovascular diseases (CVD) such as myocardial infarction and stroke (1). Evidently PAD and CVD share common risk factors which include; age, smoking, dyslipidaemia, hypertension and diabetes mellitus (2). The risk of CVD related mortality can be reduced by risk factors modifications; prescribing antiplatelet therapy, ACE inhibitors and statins to PAD patients (1). Although, PAD has many clinical presentations it can be categorised into three classes: intermittent claudication (IC), critical limb ischaemia (CLI) and asymptomatic disease (3). IC is the typical presenting symptom and is usually perceived as muscle fatigue, cramps or pain in the lower limbs (1)(3). The characteristic symptom of claudication is elevated pain upon exercise and its resolution by sufficient rest (1). In fewer cases, patients may also experience CLI, which is clinically recognised as rest pain and defined phenotypically by either ulceration and gangrene of the foot, or physiologically by a toe systolic blood pressure of <30mmHg or an ankle systolic blood pressure of <50mmHg (1)(3).

All first line treatment modalities for PAD aim to impede diseases progression and augment blood flow (4). These include behavioral modifications that aid risk factors regression and enhance exercise performance (4). If behavioral alterations fail to deliver expected results, an alternative line of treatment is revascularisation through open surgery or endovascular surgery (4). While the innovation of endovascular techniques has transformed the field of vascular treatment in PAD, it has not changed the selection of individuals that are expected to benefit from revascularization and unsurprisingly this line of therapy is proven to be highly invasive and inadequate for many PAD patients (3)(4). There remains a need for novel treatment options that can help treat PAD in a non-invasive manner. Intermittent negative pressure (INP) is one such non-invasive technique that aims to increase blood flow in ischaemic limbs. Although the idea that air pressure can be regulated to increase distal circulation was first described by

Mechanistic Insights into changes in peripheral blood flow following intermittent negative pressure.

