Two groups will be evaluated in this PhD study – healthy volunteers and PAD patients (figure 1). This will be a single-blinded placebo controlled cohort study. All healthy volunteers will receive active -40mmHg

Mechanistic Insights into changes in peripheral blood flow following intermittent negative pressure.

INP while PAD patients will receive either an active device (-40mmHg INP) or placebo device (-10mmHg INP).

Randomisation

This will be a single-blinded study. The patients will not know whether they have been assigned to the active or placebo device. The researcher will know which device a patient has been assigned to. 80 PAD patients will be recruited in total. The first 20 PAD patients will not be randomised and will be assigned the active device. The subsequent 60 PAD patients will be randomised on a 2:1 basis with 40 patients assigned the active device and 20 assigned placebo. This will allow for more mechanistic studies to be carried out on patients receiving active -40mmHg INP. Patients will be randomised to either active or placebo using an online randomisation programme.

Patients will be told which device they were assigned to at the end of the study.

At the start of the study, eligible patients with an ABPI <0.9 will be approached in wards and clinics by the study team and vascular surgery team. Patients will be given an invitation letter along with an information sheet and reply slip. The study team will offer the patients INP and the patients will be trained to use the Flow-Ox themselves.

Group 1. 40 healthy subjects will be approached by e-mail and posters at Ninewells. Healthy volunteers will be studied to explore the effects of acute application (1 session) and repeated application (daily for up to 5 days) of INP on measurements described above. Importantly for the purposes of this PhD project, this group of subjects will allow us to explore the mechanistic effects of INP on normal physiology.

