The extent of oxidative stress will be estimated by measuring reactive oxygen species (ROS) using 2',7'-dichlorodihydrofluorescein, malondialdehyde by an LC-MS assay, and reduced glutathione (GSH) and oxidised glutathione (GSSG) by a standard LC-MS assay.

The surplus blood samples will be stored for 15 years at -80°C in the department, Division of Systems Medicine at Ninewells Hospital, and will be registered with Tayside Biorepository.

Laser Doppler Imaging

Laser Doppler imaging (using the Moor Instrument FLPI system) will be used to measure microvascular endothelial functions and blood perfusion of the lower limbs and arm. This test will be a good measure of how the lower limb circulation changes after INP application and if any systemic changes in microcirculation occur in the arm. The laser will be mounted on an adjustable arm attached to a portable stand. This will be positioned 20-30 cm above the skin to capture the image. The camera records blood flow in the superficial microvessels (arterioles, venules and capillaries) up to 1mm deep in skin. Repeated scans will be obtained and the perfusion calculated in arbitrary units. The microvessels of the lower limb will be stimulated using iontophoresis of acetylcholine (ACh) and sodium nitroprusside (SNP) to assess endothelium-dependent and –independent mechanisms, respectively.

At each assessment, wounds will be photographed using the laser Doppler imager and measured using appropriate software (eg. Photoshop).

Mechanistic Insights into changes in peripheral blood flow following intermittent negative pressure.

Flow-Mediated Dilatation

This test assesses endothelial function of the macrocirculation of the (brachial artery) through flow mediated changes. This test involves using a high resolution ultrasound probe (5-8 MHz) to measure changes in the diameter of brachial artery following 5-minutes of ischaemia applied to the forearm using a blood pressure cuff inflated above systolic blood pressure (normally 200mmHg). The measurement of brachial artery diameter will be taken on three occasions; baseline, during occlusion and after deflation. This test is not anticipated to have any risk to the participants.

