A spray of glyceryl trinitrate will be given under the tongue to help assess vascular function. Glyceryl trinitrate is a medicine that is normally used in the treatment of angina (a feeling of tightness in the chest), and can cause a mild headache. Blood pressure will be checked before GTN administration. If systolic is below 100 mmHg, GTN will not be given to a participant.

Pain Chart

PAD patients, but not healthy volunteers, will be asked to fill the pain chart both before and after they use the Flow-Ox machine. In this form they will be asked to numerically rate their pain on a scale of 0-10 (ranging from no pain (0) to the worst pain they have ever felt (10)).

ABPI Monitoring

Ankle brachial pressure index (ABPI) is determined by measuring continuous systolic pressure waves at the brachial, dorsalis pedis and posterior tibial artery using a handheld 8 MHz Doppler blood velocity detector.

Arterial Stiffness (Pulse Wave Velocity and Pulse Wave Analysis)

In this non-invasive test arterial stiffness will be assessed. This test gives information of the arterial pressures that represents the systemic arterial stiffness which measures aortic pulse wave velocity and augmentation index. The participant will lie on a bed and acclimatise for 10 minutes after which blood pressure will be measured in triplicate. The waveforms of the artery from the volunteer will be recorded at the wrist (radial artery), neck (carotid artery) and groin (femoral artery) with a micro manometer using the SphygmoCor PWV and PWA system. Augmentation index, heart rate and carotid-to-femoral pulse wave velocity will be calculated by using this software. This test carries no risks for the participant health.

Mechanistic Insights into changes in peripheral blood flow following intermittent negative pressure.

STUDY POPULATION

Number of Participants

This study will recruit a total of 120 participants in total (80 PAD patients and 40 healthy volunteers).

Inclusion Criteria

PAD patients:

- Age \geq 18 years
- At the vascular outpatient clinics or admitted in ward with PAD.
- ABPI <0.9

Healthy Volunteers:

- Age \geq 18 years
- No current or previous significant cardiovascular illness
- Able to give written informed consent

Exclusion criteria

Healthy Volunteers:

- Positive medical history of:
 - ✓ Vascular diseases such as PAD, stroke, IHD, hypertension... etc.
 - ✓ Haematological conditions such as hypercoagulability, deep venous thrombosis... etc.,
- Alcohol excess

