- Unable to give written informed consent
- Pregnant women

PAD patients:

- Unable to give written informed consent
- Patients with deep venous thrombosis
- Pregnant women

Individuals will not be enrolled to the study if they are participating in the clinical phase of another interventional study or have done so within the last 30 days. Individuals who are participating in the

Mechanistic Insights into changes in peripheral blood flow following intermittent negative pressure.

follow-up phase of another interventional study, or who are enrolled in an observational study, will be co-enrolled where the CIs of each study agree that it is appropriate.

Pregnant women will not be included in the study. Pregnancy testing will be performed by research staff before the participant consents to taking part in the study.

PARTICIPANT SELECTION AND ENROLMENT

Identifying Participants

PAD patients: PAD patients will be identified by the Vascular Surgery team under the supervision of the Consultant Vascular Surgeon. The vascular clinical team will review the past medical history, drug therapy and biochemistry to ensure eligibility for the study. Patients with a diagnosis of PAD (ABPI <0.9 at rest) will be recruited into the study. They will approach PAD patients in the outpatient clinic or pre surgery hospital visit, with information about the study. Alternatively, the vascular clinical team may contact patients over the phone with information about the study then proceed to post a patient information sheet and reply slip to interested patients. Patients will be given an invitation letter, reply slip and PAD PIS. The PIS will have contact details for the patient to contact the study team with any questions or concerns about the study. The patients interested in the study will complete and return a reply slip directly to the CI/PI using a pre-paid envelope provided along with the PIS.

Healthy Volunteers: The initial approach to normal healthy subjects will take place amongst staff and students within the University of Dundee Medical School via posters displayed on notice boards around the Medical School at Ninewells and general e-mail circulations made through the School of Medicine Dean's Office. Interested volunteers will contact the research team either via email or telephone and PIS for healthy volunteers will be sent via the post or email. A minimum of 24 hours will be given prior to consent being obtained.

Consenting Participants

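### The randomised 40-versus-20 comparison is open to any PAD severity but has no planned severity adjustment or stratification; a pre-specified adjusted analysis would be a cheap improvement

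*Combined protocol and SAP*

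**What the plan says.** Under Randomisation in Study Design, the 80 PAD patients enter in two parts. For the first part, "The first 20 PAD patients will not be randomised and will be assigned the active device". For the second, "The subsequent 60 PAD patients will be randomised on a 2:1 basis with 40 patients assigned the active device and 20 assigned placebo". The method is given in one sentence: "Patients will be randomised to either active or placebo using an online randomisation programme". No section mentions a stratification factor, minimisation or blocks.

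Entry is wide. Besides age and an ABPI below 0.9, the Inclusion Criteria ask for "At the vascular outpatient clinics or admitted in ward with PAD", and Identifying Participants repeats the single threshold: "Patients with a diagnosis of PAD (ABPI <0.9 at rest) will be recruited into the study". The exclusions (consent, deep venous thrombosis, pregnancy, recent participation in another interventional study) remove no severity class. Of PAD, the Background says "it can be categorised into three classes: intermittent claudication (IC), critical limb ischaemia (CLI) and asymptomatic disease". Laser Doppler Imaging plans that "wounds will be photographed using the laser Doppler imager" at each assessment, so some patients with tissue loss are expected.

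Proposed Analyses makes within-group change the main comparison and puts the comparison between patient groups second. It lists t-tests, chi-square, ANOVA, correlation and regression, with no model or covariate named. Data Collection says that clinical data, including diagnosis and treatment, will enter the analysis, but not how.

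**The concern.** The first 20 active patients are not randomised, so the 60-versus-20 split described for Group 2 is not a fully randomised comparison. Only 40 versus 20 is. Within-group change cannot separate an effect of INP from natural course, regression to the mean or concurrent routine care over 4 to 8 weeks, so the placebo comparison carries most of the causal weight at that time point.

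Patients with rest pain or tissue loss, or in hospital, may follow a different course from stable outpatients whatever the device does. Taking change from baseline removes a difference in starting level between the arms, but not a difference in course. If the one realised allocation happens to be uneven in severity, an unadjusted comparison mixes part of that difference with the device effect, in either direction. Variation explained by severity also stays in the error term and costs precision.

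**Working it through.** **Inputs from the protocol.** 60 randomised patients, 40 active and 20 placebo. The protocol gives no figure for imbalance, severity mix or SD. Its one sample-size statement (n = 25, at least 80% power, 5% significance, 20% within-subject change) cannot be reproduced without an SD. A two-sided paired t-test would need an SD of change of 34.2 percentage points to give 80% power.

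**Assumed inputs.** Severe share among the 60: 10, 20, 30 or 40%. Gap in mean change between severe and other patients: 0.5 or 1 SD.

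**Step 1: chance of imbalance.** With K severe patients of 60, the number x in the placebo arm is hypergeometric (60, K, 20). The difference in severe share is x/20 − (K − x)/40 = (3x − K)/40, so it moves in steps of 3/40 = 7.5 points. For K = 18, balance is x = 6. A gap of 15 points or more means x ≤ 4 or x ≥ 8; a gap of 20 points or more means x ≤ 3 or x ≥ 9.

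| Severe of 60 | P(gap ≥ 15 points) | P(gap ≥ 20 points) |
|---|---|---|
| 6 (10%) | 0.165 | 0.013 |
| 12 (20%) | 0.304 | 0.083 |
| 18 (30%) | 0.370 | 0.134 |
| 24 (40%) | 0.402 | 0.161 |

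**Step 2: size of the shift.** The standard error of the arm difference is √(1/40 + 1/20) = 0.274 SD. The shift is imbalance × gap in change. At 20 points:
- gap 0.5 SD: 0.20 × 0.5 = 0.10 SD, which is 0.10/0.274 = 0.37 standard errors;
- gap 1 SD: 0.20 × 1 = 0.20 SD, which is 0.20/0.274 = 0.73 standard errors.

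**Step 3: conditional type I error.** For an unadjusted two-sided 5% z-test with a shift of b standard errors, the error rate is 1 − Φ(1.96 − b) + Φ(−1.96 − b).
- b = 0.37: 0.065, about 7%.
- b = 0.73: 0.113, about 11%.

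These rates are conditional on a 20-point imbalance having occurred. Averaged over all allocations, the rate stays at 5%.

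**Step 4: what the remedies do.** Take a between-arm difference of 20 points and SD 34.2 (both carried over from the within-subject statement, so assumptions here). The standard error is 34.2 × 0.274 = 9.37 points, and power is 57%. If the covariates explain 5 to 30% of the variance (assumed), the SD falls to 34.2 × √0.95 = 33.3 or 34.2 × √0.70 = 28.6, and power rises to 59% or 72%. In a simulation of 2:1 permuted blocks of 3 or 6 within two severity strata, the gap in severe share was zero when the strata filled their blocks, and at most 5 points with 17 severe patients.

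**The case against.** The strongest reply is that nothing here is an error. Simple 2:1 randomisation is a valid design, chance imbalance does not bias the estimate on average, and the study is exploratory with no precise power calculation. That stands, and it limits the point to an improvement.

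Several further objections also hold at least in part:
- The protocol is silent on stratification; it does not rule it out. A reader might infer that severity is deliberately ignored, but silence does not show that.
- A reader might infer that a serious imbalance is likely. At 20 points the probability is 8 to 16%, and about 1% if only 10% are severe. The shift is also below one standard error.
- The severity range is inferred from open eligibility and the planned wound measurements. The three classes in the Background describe the disease, not the expected sample. The expected mix is not given, and no passage supports a 1 SD gap in change.
- A reader might picture patients measured during an acute admission and then recovering. Ward recruitment is stated, but consent takes place at a first visit to the research department and prolonged INP is used at home, so measurement in an acute phase is not documented.
- The placebo arm is not the only control. The untreated leg is also named as one (FLOW-Ox System), although it is imperfect if INP acts systemically, which is one of the study's own questions. The measurement after a single session is little exposed to 4-to-8-week drift.
- Regression is listed and clinical data are to be used, so adjustment is possible. What is missing is a commitment to it. Because the researcher knows each assignment, covariates chosen after the data are seen would be open to doubt.

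**Conclusion.** The point holds as a modest, inexpensive improvement. The only randomised contrast has 20 placebo patients, entry is open to any severity, and neither stratification nor a severity covariate is specified. If 20 to 40% of patients are severe, a gap of 15 points or more between arms has probability about 0.30 to 0.40, and one of 20 points or more about 0.08 to 0.16. A 20-point gap would shift the comparison by 0.1 to 0.2 SD and raise the conditional type I error of an unadjusted test to about 7 to 11%, if the classes differ by 0.5 to 1 SD in change. The severe share and that gap are assumptions; with few severe patients or a small gap the effect is minor.

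A reader might conclude that the randomised comparison is biased or its type I error inflated. The documents do not support that: the allocation as described is unbiased on average with a 5% unconditional error rate. What is at stake is how the single realised allocation is interpreted, and some precision.

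**What to change.** In Proposed Analyses, pre-specify that the active-placebo comparison of the 40 and 20 randomised patients is a regression for the primary outcome (one model each for the acetylcholine and nitroprusside responses), pain and the blood markers. Adjust each model for the baseline value of that outcome and a two-level severity indicator: rest pain, ulcer, gangrene or current admission, versus all others. Record the indicator before allocation. This can be adopted even if randomisation has begun, provided it is fixed before the outcome data are examined.

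Optionally, if allocation has not begun, stratify the online 2:1 randomisation by the same indicator, with concealed and varying block sizes.

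The cost of adjustment is one extra recorded field and one or two model terms. The indicator is also coarse: it groups patients with critical ischaemia with any who are admitted for other reasons. Stratified blocks carry a further cost, since in a small stratum they make the next assignment somewhat easier for the unblinded researcher to predict, and varying the block size reduces this without removing it. Adjustment alone is therefore a reasonable choice.

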Atherosclerosis occurs when blood supply to the lower limbs is restricted upon accumulation of fat in the arteries. The initial symptom is pain in lower limbs followed by hypoxia and ulceration. The literature has indicated that intermittent negative pressure (INP) can be used to reduce the pain and facilitate wound healing. INP is a non-invasive technique that aims to increase blood flow in lower limbs and foot but there is no evidence to prove these findings. In this PhD studentship, we aim to investigate the underlying mechanisms that are involved in changes in blood flow following application of INP. The Flow-Ox 'boot' will be used to apply INP for periods ranging from 4-8 weeks, for an hour twice per day, to the lower limbs to determine the effects of INP on vascular function and blood flow. Specifically, vascular tests such as assessments of endothelial function (laser perfusion imaging with iontophoresis, flow mediated dilatation of the brachial artery), arterial stiffness (pulse wave analysis), ankle-brachial pressure index (ABPI) and blood borne metabolic and inflammatory markers will be performed before and after INP application. A pain chart will be employed before and after INP application to determine whether there is any change in perception of pain felt by individuals who suffer from pain associated with lower limb vascular disease.

INTRODUCTION

Background

Peripheral arterial disease (PAD) is a vascular condition that causes lower limb pain or discomfort (1). Diseases that facilitate stenosis or occlusion of lower limb arteries result in PAD. Atherosclerosis is a common cause for PAD as it results in the development of atherosclerotic plaque which restricts the blood supply to the lower limbs resulting in decreased oxygen transport and poor tissue perfusion (1). This creates a hypoxic environment in the lower limbs and leads to the perception of pain (1). The level of tissue damage is dependent upon the size of the obstruction and restriction of blood supply (1).

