- Investigate changes in blood flow and the relationship between changes in markers of vascular function (endothelial function & arterial stiffness) and application of INP.

Secondary Objectives:

Mechanistic Insights into changes in peripheral blood flow following intermittent negative pressure.

- Determine whether any changes in blood flow are associated with corresponding changes in blood-borne markers of endothelial activation/damage and inflammatory and oxidative stress markers.
- Determine the effects of INP on changes in markers of vascular function after acute and prolonged application.
- Determine whether the changes are confined to the local application sites or whether INP applied to one extremity exerts systemic effects on the vasculature.

To test our objectives, the specific aims are outlined below:

- Assess the changes in blood flow in the lower limbs using laser Doppler perfusion imaging before and after INP is applied. This will provide a good indication of the microcirculation. Iontophoresis of vasoactive chemicals (acetylcholine and sodium nitroprusside) will also be used to evaluate the role of endothelium-dependent and -independent mechanisms, respectively.
- Assessment of the systemic endothelial function will be measured using the flow-mediated vasodilatation (FMD) of the brachial artery. The change in FMD% will be a good indicator of the INP effect on macrovessels.
- Vascular assessment will also be recorded in the form of arterial stiffness. SpgmoCor will be used to record the peripheral pressure waveforms at carotid and femoral/radial sites in the body.
- Determine the ankle-brachial pressure index (ABPI) of PAD patients before and after INP is applied.
- Compare pain chart measurements before and after the INP procedure in patients experiencing pain associated with PAD.
- Assess levels of inflammatory and metabolic markers (E-selectin, I-CAM, VCAM, IL-1 β , IL-6, IL-10, CRP, TNF- α , Nrf2 expression, malondialdehyde, reduced & oxidised glutathione) in the blood before and after INP.

The procedures outlined above, will be applied on the first visit before INP and following 1 session (to test acute effects) and following repeated sessions for up to 8 weeks to examine the effects of prolonged applications of INP to determine the duration for optimal improvement in vascular function.

STUDY DESIGN

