For adults who lose capacity their previous wishes will remain legally binding and this will remain valid unless the protocol changes significantly. If this occurs and further consent is required from a participant who has lost capacity, the appropriate person will be asked for their consent. In all cases the CI or delegate will consult with carers and take note of any signs of objection or distress from the participant – the participant will be withdrawn if they raise objection. Where appropriate the participant will be withdrawn from any further clinical intervention and agreement will be sought from a carer to allow data collection.

The informed consent process will be conducted in compliance with TASC SOP07: Obtaining Informed Consent from Potential Participants in Clinical Research

Mechanistic Insights into changes in peripheral blood flow following intermittent negative pressure.

Ineligible and Non-recruited Participants

The reason(s) for ineligibility will be explained to participants and any questions they have will be answered. They will be thanked for their participation in screening.

Withdrawal Procedures

Participants are free to withdraw from the study at any time. If at any time the participant formally withdraws his/her consent for future participation and disclosure of future information, no further evaluations will be performed and no additional data should be collected. Data collected before withdrawal will be retained and used in the study analysis, unless the participant requests otherwise. If participants withdraw during the visit, they will have the option to request that data already collected is not to be used in the study.

STUDY & SAFETY ASSESSMENTS

Patients will undergo their standard care as routine.

PAD patients

Research bloods (40 mls) will be obtained at the research site following informed patient consent and other study procedures such as pain chart, laser imaging, arterial stiffness and ABPI. This usually will occur on the 1st day in the designated research department, Division of Systems Medicine at Ninewells Hospital, and on two follow-up visits, after one INP session and 4 to 8 weeks after daily INP use. We do not envisage that any of these will interfere with their care or are likely to cause any harm. Nevertheless, any adverse events that may potentially be related to the study will be reported to the CI and clinical Vascular Team who will administer appropriate clinical action.

Healthy Volunteers

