Data entry and checking will be undertaken by a single entry with a second look. The data entry and checking process will be decided according to risk. Data that is recorded in the CRF that is not source document in itself will be consistent with the source documents or the discrepancies explained. Checks will be made on all missing values and values out with normal or expected ranges and that values entered

Mechanistic Insights into changes in peripheral blood flow following intermittent negative pressure.

are of the correct type: i.e. numerical instead of text. Logical checks will be performed to ensure consistent reporting between relevant fields and that there are no differences between fields. Data checking will continue until all missing data and/or inconsistent values have been corrected or clarified. When data checking is complete, with no outstanding data queries, the database will be locked, using the Protect Worksheet function of EXCEL, as FINAL RESULTS. The EXCEL spreadsheet will remain archived on the Dundee University secure server for 5 years for the retention of essential documents, thereafter it will be deleted.

STATISTICS AND DATA ANALYSIS

Sample Size Calculation

As this is a PhD project exploring mechanisms of vascular changes, precise power calculations have not been obtained. The results from this PhD project will guide us regarding subsequent power calculations. However, based on our previous work exploring mechanisms of changes in vascular function using various interventions, n=25 subjects will provide at least 80% power and 5% significance to detect a 20% before and after difference within subjects in the vascular function markers proposed in this study.

Proposed Analyses

Changes in blood flow and endothelial function in the lower limbs using laser Doppler perfusion imaging and iontophoresis will be compared primarily within each group and also between patient groups at baseline, after 1 INP session and after the last INP (4 to 8 weeks) is applied. The primary outcome measure will be the change in peak blood flow response to acetylcholine and sodium nitroprusside.

Data will be analysed using widely available statistical analysis software such as SPSS. Analytical methods will include t-tests, chi-square, ANOVA, correlation and regression as appropriate.

Mechanistic Insights into changes in peripheral blood flow following intermittent negative pressure.

STUDY MANAGEMENT AND OVERSIGHT ARRANGEMENTS

Study Management

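### The top of the pain scale is the patient's own worst-ever pain, so a new lifetime-worst pain during the 4 to 8 weeks could make later scores read too low

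*Combined protocol and SAP*

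**What the plan says.** The protocol describes the pain score once, in the Pain Chart section under Study Design. PAD patients, but not healthy volunteers, "will be asked to fill the pain chart both before and after they use the Flow-Ox machine", giving a number on a scale "ranging from no pain (0) to the worst pain they have ever felt (10").

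The use of the score is set out elsewhere:

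- The opening summary gives the purpose: "to determine whether there is any change in perception of pain felt by individuals who suffer from pain".
- The specific aims under Study Objectives include: "Compare pain chart measurements before and after the INP procedure in patients experiencing pain associated with PAD".
- Study & Safety Assessments, PAD patients, lists the pain chart among the procedures for the first day and "on two follow-up visits, after one INP session and 4 to 8 weeks after daily INP use".

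On allocation, the Randomisation section gives the first 20 PAD patients the active device without randomisation. It then says: "The subsequent 60 PAD patients will be randomised on a 2:1 basis with 40 patients assigned the active device and 20 assigned placebo".

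Proposed Analyses names a different primary outcome: "The primary outcome measure will be the change in peak blood flow response to acetylcholine and sodium nitroprusside".

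**The concern.** A score that is compared over time needs end points that keep their meaning between visits. Here the upper end point is the patient's personal maximum to date. Read literally, that maximum can rise during follow-up but cannot fall. If it rises, 10 stands for more pain than it did at baseline, and every lower score is stretched with it. A patient with unchanged pain then gives a lower number, and a patient whose pain has worsened may give the same number.

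The population makes such an event plausible. Patients may be recruited "At the vascular outpatient clinics or admitted in ward with PAD", or approached at a visit before surgery, and critical limb ischaemia is not among the listed exclusions for PAD patients. No section fixes the anchor at baseline, lets patients see their earlier score, or records whether a new worst pain occurred between visits. A drift of this kind could therefore not be recognised or corrected afterwards.

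At stake is the reading of the pain change at 4 to 8 weeks as relief. The first 20 patients matter most here, because they have no concurrent placebo patients against whom drift could be seen.

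**Working it through.** **No plan figure to reproduce.** The documents give no effect size, standard deviation or sample size for pain. The only power statement (n=25, a 20% within-subject difference) concerns the vascular markers and plays no part here.

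**Inputs from the protocol.** The 0 to 10 scale and its anchors come from Pain Chart. The repeat assessment after one session and at 4 to 8 weeks comes from Study & Safety Assessments. The comparison over time comes from the specific aims.

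**Assumptions, not in the documents.** Pain has an intensity P on a notional fixed 0 to 100 scale. The patient rates pain at the time of completion; the Pain Chart section does not state which pain is rated. The patient applies the anchor literally. With A the worst pain felt so far:

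score = 10 × P / A

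**Step 1: single patient.** Baseline P = 30 and A = 60 give 10 × 30/60 = 5.0. A new worst pain of 80 then occurs.

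- Pain unchanged at 30: 10 × 30/80 = 3.75. This is an apparent fall of 1.25 points, or 1.25/5.0 = 25%, with no true change.
- Pain worse, at 40: 10 × 40/80 = 5.0, recorded as no change. On the baseline anchor it would have been 10 × 40/60 = 6.7.

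**Step 2: dependence on the size of the rise.** Let r be the new worst pain divided by the old, and take a baseline score of 6. The later score is 6 × (true change in pain) / r.

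| r (assumed) | pain unchanged | pain 10% worse | pain 25% worse |
|---|---|---|---|
| 1.00 (anchor stable) | 6.0 | 6.6 | 7.5 |
| 1.10 | 5.5 | 6.0 | 6.8 |
| 1.25 | 4.8 | 5.3 | 6.0 |
| 1.50 | 4.0 | 4.4 | 5.0 |

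Worse pain reads as unchanged when the anchor rises in the same proportion as the pain, and as improved when the anchor rises by more.

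**Step 3: group mean.** If a share f of patients with baseline score 6 has such an event and true pain is unchanged, the mean falls by f × 6 × (1 − 1/r).

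- f = 5%: 0.03, 0.06 and 0.10 points for r = 1.10, 1.25 and 1.50.
- f = 30%: 0.16, 0.36 and 0.60 points for the same r.
- f = 1% with r = 1.25: 0.01 × 1.2 = 0.012 points.

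Both f and r are assumed, so these results only restate the assumptions. They show that the mean shift is negligible if such events are rare, although an affected patient's own score can move by 0.5 to 2.0 points (6 − 5.5 to 6 − 4.0).

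**Step 4: which comparisons are exposed.** The comparison around one session leaves little time for a new lifetime-worst pain. The change from baseline to 4 to 8 weeks leaves several weeks. An active-placebo comparison of that change would be biased only if such events differed between arms, because an equal shift in both cancels in the difference.

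**The case against.** The strongest reply is that the trigger is demanding. The anchor is not limited to leg pain, so past surgery or injury counts, and a merely bad episode within 4 to 8 weeks does not move it. The pain must exceed anything the patient has ever felt, and the documents give no frequency for that. Few patients may rate by forming a literal ratio. This all stands. It limits the size of the problem but does not fix the anchor.

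A reader might also infer several stronger things that the documents do not support:

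- **That the net error must run towards benefit, or favour the arm with more severe episodes.** The literal maximum can only rise, but patients rate against a remembered pain, and memory can fade. A severe episode may also leave current pain higher. The net direction, overall or by arm, is not determined.
- **That the active-placebo result for pain is compromised.** The between-group sentence in Proposed Analyses covers the laser Doppler and iontophoresis measures. The aim for pain states only a comparison over time.
- **That the cap at 10 is peculiar to this anchor.** A patient at 10 who worsens stays at 10 on any 0 to 10 scale, including one with a different anchor.

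Two further points stand. 'Worst pain imaginable' is itself subjective, and a severe new experience might shift it too; its advantage is only that follow-up events do not define it. The printed chart is not in the text available, so the wording patients actually see cannot be checked.

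**Conclusion.** The point holds as a minor weakness in measurement. As the Pain Chart section is worded, a new lifetime-worst pain during follow-up can lower a later score when pain is unchanged, or leave worsening unseen. This concerns mainly the within-patient change from baseline to 4 to 8 weeks, including that of the first 20 active patients.

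The sizes rest on two things the documents do not establish: that patients apply the anchor literally, and how often and by how much a worst-ever pain is exceeded. They show how the mechanism works and should not be read as an estimate of bias in this trial. Pain is one of the specific aims and not the primary outcome, so the primary analysis and the power statement are untouched.

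**What to change.** In the Pain Chart section and on the chart itself, replace the upper anchor with one not defined by the patient's own pain history, for example '10 = worst pain imaginable', and use identical wording at every visit.

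The cost is one phrase in the protocol and on the form, with the usual amendment approval. No visit, assessment or participant is added. The new anchor remains subjective and does not remove the ceiling at 10. Patients already scored on the present wording should keep it to their last visit, so that each patient's scores share one anchor, and should be flagged in the analysis so that the two wordings are not pooled unmarked.
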